**Table 8: Derivation of irRC overall responses**

| Measurable response                                  | Nonmeasurable response  | Nonmeasurable response     | Overall response  |
|--|-------------------------|----------------------------|-------------------|
| Index and new, measurable lesions (tumor burden)*, % | Non-index lesions       | New, nonmeasurable lesions | Using irRC        |
| ↓100   | Absent                  | Absent                     | irCR † |
| ↓100   | Stable                  | Any                        | irPR † |
| ↓100   | Unequivocal progression | Any                        | irPR † |
| ↓≥50   | Absent/stable           | Any                        | irPR † |
| ↓≥50   | Unequivocal progression | Any                        | irPR † |

|              |                         |     |                   |
|--------------|-------------------------|-----|-------------------|
| ↓<50 to <25↑ | Absent/stable           | Any | irSD              |
| ↓<50 to <25↑ | Unequivocal progression | Any | irSD              |
| ≥25          | Any                     | Any | irPD † |

\*Decreases assessed relative to baseline, including measurable lesions only (>5 × 5 mm).

†Assuming response (irCR) and progression (irPD) are confirmed by a second, consecutive assessment at least 4 wk apart.

#### 7.1.2.6.6 Method of assessment

The same method of assessment and the same technique will be used whenever possible to characterize each identified and reported lesion at baseline and during follow-up. Imaging-based evaluation is preferred to evaluation by clinical examination when both methods have been used to assess the antitumor effect of a treatment.

**Chest x-ray-** Lesions on chest x-ray are acceptable as measurable lesions when they are clearly defined and surrounded by aerated lung. However, CT is preferable.

**Conventional CT and MRI-** These techniques will be performed with cuts of 10 mm or less in slice thickness contiguously. Spiral CT will be performed using a 5 mm contiguous reconstruction algorithm. This applies to tumors of the chest, abdomen, and pelvis.

**Ultrasound (US)-** Because one of the endpoints of the study is objective response evaluation, US will not be used to measure tumor lesions. US might be used, at the discretion of the investigator, to confirm the complete disappearance of superficial lesions assessed by clinical examination.

**Cytology, histology-** These techniques may be used to differentiate between partial responses (PR) and complete responses (CR) if necessary and determined by the investigator. Cytological confirmation of the neoplastic origin of any effusion that appears or worsens during treatment when the measurable tumor has met criteria for response or stable disease is mandatory to differentiate between response or stable disease (an effusion may be a side effect of the treatment) and progressive disease.

#### 7.1.2.6.7 Definitions Associated with Response Evaluation Criteria in Solid Tumors (RECIST) version 1.1

### Measurable disease

The presence of at least one measurable lesion. If the measurable disease is restricted to a solitary lesion, its neoplastic nature should be confirmed by cytology/histology.

### Measurable lesions

Measurable lesions are defined as those that can be accurately measured in at least one dimension (longest diameter to be recorded) as >20 mm by chest x-ray, as >10 mm with CT scan, or >10 mm with calipers by clinical exam. All tumor measurements must be recorded in millimeters (or decimal fractions of centimeters).

### Non-measurable lesions

All other lesions (or sites of disease), including small lesions (longest diameter <10 mm or pathological lymph nodes with  $\geq 10$  to <15 mm short axis), are considered non-measurable disease. Bone lesions, leptomeningeal disease, ascites, pleural/pericardial effusions, lymphangitis cutis/pulmonitis, inflammatory breast disease, and abdominal masses (not followed by CT or MRI), are considered as non-measurable.

**Note:** Cystic lesions that meet the criteria for radiographically defined simple cysts should not be considered as malignant lesions (neither measurable nor non-measurable) since they are, by definition, simple cysts.

'Cystic lesions' thought to represent cystic metastases can be considered as measurable lesions, if they meet the definition of measurability described above. However, if non-cystic lesions are present in the same subject, these are preferred for selection as target lesions.

### Malignant lymph nodes

To be considered pathologically enlarged and measurable, a lymph node must be >15 mm in short axis when assessed by CT scan (CT scan slice thickness recommended to be no greater than 5 mm). At baseline and in follow-up, only the short axis will be measured and followed.

### Baseline documentation of "Target" and "Non-Target" lesions

#### Target lesions.

All measurable lesions up to a maximum of 2 lesions per organ and 5 lesions in total, representative of all involved organs, should be identified as **target lesions** and recorded and measured at baseline. Target lesions should be selected on the basis of their size (lesions with the longest diameter), be representative of all involved organs, but in addition should be those that lend themselves to reproducible repeated measurements. It may be the case that, on occasion, the largest lesion does not lend itself to reproducible measurement in which circumstance the next largest lesion which can be measured reproducibly should be selected. A sum of the diameters (longest for non-nodal lesions, short axis for nodal lesions) for all target lesions will be calculated and reported as the baseline sum diameters. If lymph nodes are to be included in the sum, then only the short axis is added into the sum. The baseline sum diameters will be used as reference to further characterize any objective tumor regression in the measurable dimension of the disease.

### 7.1.2.6.8 Evaluation of Target Lesions: Table 9

|                           |  |
|---------------------------|--|
| Complete Response (CR):   | Disappearance of all target lesions  |
| Partial Response (PR):    | At least a 30% decrease in the sum of the longest diameter (LD) of target lesions, taking as reference the baseline sum LD.  |
| Progressive Disease (PD): | At least a 20% increase in the sum of the LD of target lesions, taking as reference the smallest sum LD recorded since the treatment started or the appearance of one or more new lesions. |
| Stable Disease (SD):      | Neither sufficient shrinkage to qualify for PR nor sufficient increase to qualify for PD, taking as reference the smallest sum LD since the treatment started.                             |

### 7.1.2.6.9 Evaluation of Non-Target Lesions: Table 10

|   |   |
|---|---|
| Complete Response (CR):   | Disappearance of all non-target lesions and *normalization of tumor marker level.                                 |
| Incomplete Response/
Stable Disease (SD):  | Persistence of one or more non-target lesion(s) and/or maintenance of tumor marker level above the normal limits. |
| Progressive Disease (PD):   | Appearance of one or more new lesions and/or unequivocal progression of existing non-target lesions.              |
| Although a clear progression of "non-target" lesions only is exceptional, in such circumstances the opinion of the investigator will prevail.         |   |
| *Note: If tumor markers are initially above the upper normal limit, they must normalize for a patient to be considered in complete clinical response. |   |

### 7.1.2.6.10 Evaluation of Best Overall Response: Table 11

The best overall response is the best response recorded from the start of the treatment until disease progression/recurrence (taking as reference for progressive disease the smallest measurements recorded since the treatment started). The patient's best response assignment will depend on the achievement of both measurement and confirmation criteria.

[REDACTED] IRB  
IRB ID: [REDACTED]  
Approval Date: [REDACTED]  
Expiration Date: [REDACTED]

| Target Lesions | Non-Target Lesions     | New Lesions | Overall Response |
|----------------|------------------------|-------------|------------------|
| CR             | CR                     | No          | CR               |
| CR             | Incomplete response/SD | No          | PR               |
| PR             | Non-PD                 | No          | PR               |
| SD             | Non-PD                 | No          | SD               |
| PD             | Any                    | Yes or No   | PD               |
| Any            | PD                     | Yes or No   | PD               |
| Any            | Any                    | Yes         | PD               |

Notes:

Patients with a global deterioration of health status requiring discontinuation of treatment without objective evidence of disease progression at that time should be classified as having “symptomatic deterioration.” Every effort will be made to document the objective progression.

In some circumstances, it may be difficult to distinguish residual disease from normal tissue. When the evaluation of complete response depends on this determination, the residual lesion will be investigated (fine needle aspirate/biopsy if possible) before confirming the complete response status.

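### Table 9 judges response on a sum of longest diameters that conflicts with the protocol's short-axis rule for nodes, gives nodal targets no rule for CR, and sets no minimum increase in mm for PD

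*Combined protocol and SAP*

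**What the plan says.** Three subsections of 7.1.2.6.7 set the nodal rules.

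- Malignant lymph nodes: to be measurable, "a lymph node must be >15 mm in short axis when assessed by CT scan", and "At baseline and in follow-up, only the short axis will be measured and followed".
- Target lesions: "A sum of the diameters (longest for non-nodal lesions, short axis for nodal lesions) for all target lesions will be calculated", and this is the baseline reference.
- Non-measurable lesions: the list includes "small lesions (longest diameter <10 mm or pathological lymph nodes with" a short axis of at least 10 mm but under 15 mm. This implies, without saying so, that a node under 10 mm is not pathological.

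Table 9 in Section 7.1.2.6.8 follows directly.

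- CR is "Disappearance of all target lesions".
- PR is "At least a 30% decrease in the sum of the longest diameter (LD) of target lesions, taking as reference the baseline sum LD".
- PD is "At least a 20% increase in the sum of the LD of target lesions, taking as reference the smallest sum LD recorded" since treatment started, or a new lesion. SD is whatever meets neither PR nor PD.

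The notes under Table 11 (Section 7.1.2.6.10) add that, where residual disease is hard to tell from normal tissue, the residual lesion is aspirated or biopsied if possible before CR is confirmed. Section 11.3 adopts RECIST 1.1 as published. No section says whether that publication or Table 9 prevails.

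**The concern.** Table 9 uses a different quantity from the one defined immediately above it. Both sums may be available to a site: Section 7.1.2.6 has the same lesions followed by irRC, and irRC uses the two largest perpendicular diameters. In a multi-center trial, two readers could therefore score one scan differently, each following the protocol.

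Two further gaps concern small residuals, which effective chemoradiation may leave. CR makes no allowance for a target node that has returned to normal size. PD is purely proportional, so the absolute change that triggers it shrinks with the nadir.

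RECIST 1.1 feeds secondary PFS (Section 7.1.2.6), which Section 8.2 compares with historical controls by a one-sample log-rank test. Section 8.2 counts any sign of progression and asks for no confirmation, so one spurious PD could become a PFS event. RECIST CR also opens one of the two retreatment branches in Section 7.1.5.5.

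**Working it through.** The plan gives no figure to reproduce here. Lesion sizes, error SD and number of scans below are assumptions; the thresholds are the plan's.

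**1. Which diameter is summed.** Assume a primary of 40 mm falling to 30 mm, and a node of 16 x 28 mm falling to 9 x 22 mm.

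- Short-axis sum: 40 + 16 = 56, then 30 + 9 = 39. Change 39/56 - 1 = -30.4%, which is PR.
- Longest-diameter sum: 40 + 28 = 68, then 30 + 22 = 52. Change 52/68 - 1 = -23.5%, which is SD.

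The call does not always differ. With the primary at 28 mm and the node at 12 x 22 mm on follow-up, the changes are 40/56 - 1 = -28.6% and 50/68 - 1 = -26.5%, both SD.

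**2. Nodal CR.** A sole target node falling from 16 to 8 mm short axis changes by (8 - 16)/16 = -50%. It is now under the 10 mm from which the protocol treats nodes as pathological. It has not disappeared, so Table 9 read literally gives PR.

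**3. PD trigger.** Rise needed = 0.20 x nadir sum.

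| Nadir sum (mm) | 8 | 10 | 15 | 25 |
|---|---|---|---|---|
| Rise for PD (mm) | 1.6 | 2 | 3 | 5 |

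A sole target node can be PD while still under 10 mm only if its nadir is below 10/1.2 = 8.33 mm. If an 8 mm node is summed with other targets, the trigger grows:

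| Other targets at nadir (mm) | 10 | 20 | 30 | 40 |
|---|---|---|---|---|
| Rise for PD (mm) | 3.6 | 5.6 | 7.6 | 9.6 |
| A 1.6 mm change as % of the sum | 8.9 | 5.7 | 4.2 | 3.3 |

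**4. False PD in an unchanged residual.** Simulation of 200,000 series of 7 measurements, with independent normal error in the sum and the running minimum as reference. Entries are the percentage with at least one crossing, without / with an added 5 mm minimum increase.

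| Error SD | Sum 10 mm | Sum 15 mm | Sum 25 mm |
|---|---|---|---|
| 0.5 mm | 8 / 0 | about 0 / 0 | 0 / 0 |
| 1 mm | 70 / 0.4 | 31 / 0.4 | 1 / 0.4 |
| 1.5 mm | 90 / 13 | 70 / 13 | 21 / 13 |

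From about 30 mm the two rules give identical rates, because 20% of the reference is then nearly always above 5 mm.

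If the next scan must also be at least 20% above the same reference, the rates without a floor at SD 1 to 1.5 mm fall to 28-54% at 10 mm, 7-28% at 15 mm and 0.1-4% at 25 mm.

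**The case against.** The strongest reply is that LD in Table 9 is loose shorthand for the sum defined just above it, and that Section 11.3 adopts RECIST 1.1 anyway. Many readers would take it so. But the short-axis rule and Table 9 cannot both be followed literally, and nothing in the documents ranks them.

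Other objections stand, and limit the point:

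- A reader might infer that any 1.6 mm change in a normal-sized node is PD. That holds only for a node as sole target with an assumed 8 mm nadir.
- A reader might infer that patients with nodal targets can hardly reach CR. The residual-lesion note under Table 11 gives a route, though it is qualified and sets no node size.
- The bare 20% contradicts no nodal rule printed in the protocol. No section sets a minimum rise, and the published RECIST 1.1 text is cited but not reproduced. This part is a weakness in robustness.
- Section 7.1.2.6.6 states "Spiral CT will be performed using a 5 mm contiguous reconstruction algorithm". That describes image reconstruction. It does not measure the error of an in-plane diameter, so it does not show that the trigger is below measurement resolution.
- Survival follow-up (Section 7.1.5.4.1) and retreatment (Section 7.1.5.5) require confirmed progression, so an isolated false PD should not by itself move a patient. Retreatment also has a second branch, open to SD, PR or CR after 18 doses.
- The documents do not give the criteria used for the historical controls, so the net bias in that comparison cannot be stated. Nor do they show how many patients would have sums below 25 mm.

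**Conclusion.** The point holds in three parts of unequal strength.

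1. The conflict over which diameter is summed is plain on the page and can change a PR/SD call.
2. The missing nodal CR rule is a gap in the literal wording, partly covered by the aspirate or biopsy note.
3. The missing minimum increase matters only for small total residual sums. Its size depends on an error SD that the documents do not give: 8% to 90% false crossings at 10 mm for an SD of 0.5 to 1.5 mm, and no difference between the rules from about 30 mm.

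The effect falls on RECIST response and secondary PFS. A reader might infer that dose finding is affected, since Section 7.1.2.6 says RECIST 1.1 determines the primary objective. Section 8.1, however, bases escalation and the MTD on DLT alone, defined as grade 4 pneumonitis. The matter should be corrected, but it does not undermine the trial's main decision.

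**What to change.** Reconcile Table 9 with Section 7.1.2.6.7 and with RECIST 1.1 as adopted in Section 11.3:

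- Word PR, SD and PD on the sum of diameters already defined above the table.
- State how a nodal target counts toward CR, consistently with the 10 mm short-axis limit under Non-measurable lesions.
- Add a minimum absolute increase to PD, for example 5 mm, after checking the value against the cited RECIST 1.1 text.
- State that the revised text governs over any conflicting wording.
- Re-derive existing RECIST calls from recorded measurements.

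The cost is one table and a re-read of recorded data, with no new patients or scans. Re-derivation is complete only where later scans exist: a patient already moved to telephone follow-up after a PD call may have none, and such cases should be listed. The downside is that a few true progressions on very small residuals will be dated one scan later.

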**7.1.2.7 Tumor Tissue Collection and Correlative Studies Blood Sampling**

Mandatory submission of unstained slides from an archived tumor block for PD-L1 analysis. Sites must verify that an archived tumor block is available to obtain unstained slides from prior to registration to the trial. Unstained slides submitted for PD-L1 staining must be cut and sent within 7 days of analysis. A fresh biopsy is NOT mandatory to participate in this trial.

A fine needle aspirate, frozen sample, plastic embedded sample, cell block, clot, bone, bone marrow or cytologic specimen are not be acceptable for PD-L1 analysis.  
Please refer to the Study Procedures Manual for processing, labeling and shipping instructions.

### 7.1.3 Laboratory Procedures/Assessments

Details regarding specific laboratory procedures/assessments to be performed in this trial are provided below. Laboratory Safety Evaluations (Hematology, Chemistry and Urinalysis)

Laboratory tests for hematology, chemistry, and others are specified in Table 5.

Table 12 Laboratory Tests

| Hematology   | Chemistry   | Other                                  |
|--|---|--|
| Hematocrit   | Albumin   | Serum β-human chorionic gonadotropin † |
| Hemoglobin   | Alkaline phosphatase  | (β-hCG) †                              |
| Platelet count   | Alanine aminotransferase (ALT)  | PT (INR)                               |
| WBC (total and differential)   | Aspartate aminotransferase (AST)  | aPTT                                   |
| Red Blood Cell Count   | Lactate dehydrogenase (LDH)   | Total triiodothyronine (T3)            |
| Absolute Neutrophil Count  | Carbon Dioxide ‡  | Free tyroxine (T4)                     |
| Absolute Lymphocyte Count  | (CO 2 or bicarbonate)  | Thyroid stimulating hormone (TSH)      |
|  | Uric Acid   | PK                                     |
|  | Calcium   | Blood for correlative studies          |
|  | Chloride  |  |
|  | Glucose   |  |
|  | Phosphorus  |  |
|  | Potassium   |  |
|  | Sodium  |  |
|  | Magnesium   |  |
|  | Total Bilirubin   |  |
|  | Direct Bilirubin (If total bilirubin is elevated above the upper limit of normal) |  |
|  | Total protein   |  |
|  | Blood Urea Nitrogen   |  |
| † Perform on women of childbearing potential only.
‡ If considered standard of care in your region. |   |  |

[REDACTED] IRB  
 [REDACTED] IRB  
 Approval Date:  
 Expiration Date:

Laboratory tests for screening or entry into the Second Course Phase should be performed within 10 days prior to the first dose of treatment. After Cycle 1, pre-dose laboratory procedures can be conducted up to 72 hours prior to dosing. Results must be reviewed by the investigator or qualified designee and found to be acceptable prior to each dose of trial treatment.

#### **7.1.3.1 Pharmacokinetic/Pharmacodynamic Evaluations**

As PK data have previously been examined in other clinical trials, we do not anticipate the need to perform PK testing unless otherwise directed by the Sponsor.

##### **7.1.3.1.1 Blood Collection for Serum Pembrolizumab**

Sample collection, storage and shipment instructions for serum samples will be provided in the Laboratory Manual.

The timepoints for PK blood sampling are described in Section 6 – Trial Flow Chart.

##### **7.1.3.1.2 Blood Collection for Anti-Pembrolizumab Antibodies**

Sample collection, storage and shipment instructions for blood samples will be provided in the Laboratory Manual.

#### **7.1.4 Other Procedures**

##### **7.1.4.1 Withdrawal/Discontinuation**

When a subject discontinues/withdraws prior to trial completion, all applicable activities scheduled for the final trial visit should be performed at the time of discontinuation. Any adverse events which are present at the time of discontinuation/withdrawal should be followed in accordance with the safety requirements outlined in Section 7.2 - Assessing and Recording Adverse Events. Subjects who a) attain a CR or b) complete 36 doses of treatment with pembrolizumab may discontinue treatment with the option of restarting treatment if they meet the criteria specified in Section 7.1.5.5. After discontinuing treatment following assessment of CR, these subjects should return to the site for a Safety Follow-up Visit (described in Section 7.1.5.3.1) and then proceed to the Follow-Up Period of the study (described in Section 7.1.5.4).

##### **7.1.4.2 Blinding/Unblinding**

This is an open label trial; there is no blinding for this trial.

#### **7.1.5 Visit Requirements**

Visit requirements are outlined in Section 6.0 - Trial Flow Chart. Specific procedure-related details are provided above in Section 7.1 - Trial Procedures.

### 7.1.5.1 Screening

Approximately 28 days before beginning treatment, potential subjects will be evaluated to determine if they fulfill the eligibility criteria. Tests performed before the subject signs consent are permitted as long as they are performed within the appropriate time frame as per the trial flow chart. Subjects may be rescreened after failing to meet the inclusion/exclusion criteria. Please see the trial flow chart is in Section 6.1.

#### 7.1.5.1.1 Screening Period

The screening period may last from 1-28 days as long as the subject is able to have necessary testing completed in the appropriate time frames.

### 7.1.5.2 Treatment Period

Section 6.1 details the treatment period, consisting of 6 weeks of chemoradiation therapy and then initiation of the pembrolizumab every 3 weeks for up to 18 cycles. Pembrolizumab will be incorporated during chemoradiation by the phase I trial.

### 7.1.5.3 Post-Treatment Visits

#### 7.1.5.3.1 Safety Follow-Up Visit

The mandatory Safety Follow-Up Visit should be conducted approximately 30 days after the last dose of trial treatment or before the initiation of a new anti-cancer treatment, whichever comes first. All AEs that occur prior to the Safety Follow-Up Visit should be recorded. Subjects with an AE of Grade > 1 will be followed until the resolution of the AE to Grade 0-1 or until the beginning of a new anti-neoplastic therapy, whichever occurs first. SAEs that occur within 90 days of the end of treatment or before initiation of a new anti-cancer treatment should also be followed and recorded. Subjects who are eligible for retreatment with pembrolizumab (as described in Section 7.1.5.5) may have up to two safety follow-up visits, one after the Treatment Period and one after the Second Course Phase.

